6.3 Demography and Baseline Disease Characteristic

6.3.1 Summary of Demographic information

The demographic information of age, gender, ethnicity, race, height, weight, and body mass index (BMI) at baseline will be summarized by treatment group and overall. In addition, the associated listing will be provided. The demographic will be summarized for the MITT population only – note that if the safety population differs from the MITT population (i.e. if not all subjects receive their randomized treatment) then the summaries will be repeated for the safety population.

6.3.2 Baseline Disease Characteristics

6.3.2.1 GAP score

As a disease characteristic, GAP score [[Ley 2012](#)] is an 8-point score (0-8) and calculated from age, gender, baseline percent predicted FVC and percent predicted DLco corrected for hemoglobin (DL_{co}/Hb) at baseline visit. The calculation is described in Table 2 as follows.

Table 2: GAP Score Calculation

	Calculation
Gender	
 If female, add 0 point.

	
 If male, add 1 point.
Age	
 If Age ≤ 60, add 0 point If $61 \leq \text{Age} \leq 65$, add 1 point If Age > 65, add 2 points
Baseline percent (%) predicted FVC	
 If % predicted FVC > 75, add 0 point If $50 \leq \%$ predicted FVC ≤ 75, add 1 point If % predicted FVC < 50, add 2 points
Percent (%) predicted DL _{co} /Hb at baseline visit	
 If % predicted DL_{co}/Hb > 55, add 0 point If $36 \leq \%$ predicted DL_{co}/Hb ≤ 55, add 1 point If % predicted DL_{co}/Hb ≤ 35, add 2 points If DL_{CO} cannot be performed at baseline visit, add 3 points. If the % predicted DL_{co}/Hb is missing due to the unacceptable values through the ERT best test review (BTR) quality control process or hemoglobin missing, the defined baseline % predicted DL_{co}/Hb, the latest non-missing % predicted DL_{co}/Hb before first dosing, will be applied.

6.3.2.2 Summary of Baseline Disease Characteristics

Baseline disease characteristics information of ex-smoker status, randomization stratum (on/off background therapy), region, GAP score, GAP score category (0-3, 4-5 and 6-8), FVC (mL), percent predicted FVC (%), forced expiratory volume over 1 second (FEV₁, L), FEV₁/FVC, absolute DL_{co} corrected for hemoglobin (DL_{co}/Hb, mL/min/mmHG), percent Predicted DL_{co}/Hb (%), total lung capacity (TLC, L), residual volume (RV, L) will be summarized by treatment group and overall.

The baseline characteristics will be summarized for the MITT population only – note that if the safety population differs from the MITT population, then the summaries will be repeated for the safety population.

6.4 Concomitant Therapy

A concomitant therapy is any drug or substance administered between the time a subject is screened for the study and the final study visit.

In order to define concomitant for therapies with missing start or stop date, the following additional criteria are defined:

- If both the start and stop dates of a therapy are missing, then the therapy will be considered concomitant;
- If the start date is missing and the stop date of the therapy falls on/after the screening visit, then the therapy will be considered concomitant;

- If the start date of a therapy is prior to the date of the screening and the stop date of the therapy is missing and the therapy is listed as ongoing, that therapy will be considered concomitant;
- If the start date of a therapy is prior to the date of screening and the stop date of that therapy is missing and the therapy is not listed as ongoing, that therapy will be considered non-concomitant.

For a record with a partial start/end date, the year/month of the partial date will be compared to screening to determine whether it is concomitant.

All concomitant medications will be coded using the World Health Organization (WHO) medication dictionary. All concomitant non-drug treatments will be coded using the MedDRA dictionary.

The number and percent of subjects taking concomitant medication, non-drug treatments will be summarized by treatment group.

6.5 Study Drug Exposure and Study Drug Compliance

Number of weeks on study treatment (BG00011 or placebo), calculated as

Duration of treatment exposure (weeks) = (date of the last dose – date of the first dose +1)/7, will be summarized as a categorical variable with the following cumulative duration of exposure categories: at least 4, 8, 12, 16, 20, 26, 32, 38, 44, 52 weeks.

In addition, the duration of treatment exposure (weeks) will be summarized as continuous variable with summary statistics.

The first dose of BG00011 or placebo (study treatment) will be administered at the study site during the Baseline Visit. All subsequent doses should be administered by the subject or the subject's caregiver. Compliance with study treatment dosing is to be documented by the subject or the subject's caregiver in the electronic study diary and monitored at each study visit by study site personnel.

Overall compliance for each subject will be assessed based on the dosing recorded in the electronic study diary along with the first dose recorded in the eCRF. The compliance will be calculated and summarized as a continuous variable for each treatment group and background status. The compliance will be calculated using the following formula:

Percent Compliance = (actual number of doses administered)/(number of doses expected to be administered) * 100

For all subjects who did not reach week 52 visits whether due to the study early termination and/or treatment discontinuation, "number of doses expected" will be relative to the time of discontinuation.

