The information contained herein may not be used, disclosed, or published without the written consent of Biogen MA Inc.

Period	Screening Period	Placebo-Controlled Treatment Period												Safety Follow-Up	Unscheduled
Study Visit	Screening ¹	Baseline	Day 5 ²	Week 4	Week 8	Week 12	Week 16	Week 20	Week 26	Week 32	Week 38	Week 44	Week 52/ EoT ³	Week 60	IPF Exacerbation
Study Day	≤35 days prior to Baseline	0	5	28	56	84	112	140	182	224	266	308	364	420	NA
Visit Window (Days)	NA	NA	+1	±3	±3	±3	±3	±3	±7	±7	±7	±7	±7	±7	NA
Serum for anti-BG00011 antibodies		X		X		X			X		X			X	
Study diary training, administration, and review		X													
Subject completion of study diary ¹⁸		-----Ongoing throughout the study-----													
Administration of study treatment in clinic		X ¹⁹													
Injection training		X	-----Injection retraining to be offered as necessary-----												
Weekly administration of study treatment			To be performed by subject or caregiver once weekly from Week 1 (second dose) through Week 51 (final dose)												
Dispense and/or collect study treatment		X		X	X	X	X	X	X	X	X	X	X		

CONFIDENTIAL

The information contained herein may not be used, disclosed, or published without the written consent of Biogen MA Inc.

Period	Screening Period	Placebo-Controlled Treatment Period												Safety Follow-Up	Unscheduled
Study Visit	Screening ¹	Baseline	Day 5 ²	Week 4	Week 8	Week 12	Week 16	Week 20	Week 26	Week 32	Week 38	Week 44	Week 52/EoT ³	Week 60	IPF Exacerbation
Study Day	≤35 days prior to Baseline	0	5	28	56	84	112	140	182	224	266	308	364	420	NA
Visit Window (Days)	NA	NA	+1	±3	±3	±3	±3	±3	±7	±7	±7	±7	±7	±7	NA
Compliance/drug accountability				X	X	X	X	X	X	X	X	X	X	X	
Adverse event reporting ²⁰		-----Monitor and record throughout Treatment and Follow-Up Periods -----													
Serious adverse event reporting		-----Monitor and record throughout the study -----													
Concomitant therapy and procedures recording ²¹		-----Monitor and record throughout the study -----													

Abbreviations not already defined in the table: anti-HBc = total hepatitis B core antibody; anti-HBs = hepatitis B surface antibody; EoT = End of Treatment; FEV = forced expiratory volume; FEV₁ = forced expiratory volume over 1 second; FVC = forced vital capacity; HBsAg = hepatitis B surface antigen; HCV = hepatitis C virus; HIV = human immunodeficiency virus; IPF = idiopathic pulmonary fibrosis; NA = not applicable; PK = pharmacokinetics.

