7. STUDY DESIGN

7.1. Study Overview

This is a Phase 2b randomized, double-blind, placebo-controlled study designed to evaluate the efficacy, safety, PK, and tolerability of BG00011 in subjects with IPF. The study will be conducted at approximately 100 sites in up to 20 countries in North America, Europe, and Rest of World. Approximately 290 subjects are planned to be randomized.

To be eligible for the study, subjects must have a diagnosis of IPF consistent with current ATS/ERS/JRS/ALAT guidelines (Section 4.2, Table 1, and Figure 1). Eligibility for the study will be determined centrally. In addition, features of IPF at Screening must include: FVC \geq 50% of predicted value; DL_{CO} (corrected for hemoglobin) \geq 30% of predicted value; oxygen saturation \geq 90% at rest (receiving \leq 2 L/min of supplemental oxygen). Subjects with IPF who do not otherwise qualify for study eligibility may be rescreened once at the discretion of the Principal Investigator.

Subjects will be stratified by background therapy status (subjects receiving background therapy and subjects not receiving background therapy) and randomized in a 1:1 ratio of BG00011 to placebo (Figure 4). Enrollment will also be monitored to ensure that subjects receiving background therapy represent approximately 50% of each treatment group.

Subjects will receive weekly injections of BG00011 or placebo, as a solution for SC injection in a prefilled syringe, for 52 consecutive weeks (a total of 52 doses). The first dose will be administered at the Baseline (Day 0) Visit. The rest of the doses may be administered independently (e.g., not at the study site) by the subject or the subject's caregiver.

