10. DISCONTINUATION OF STUDY TREATMENT AND WITHDRAWAL OF SUBJECTS FROM THE STUDY

10.1. Discontinuation of Study Treatment

Study treatment discontinuation is defined as the premature ending of study treatment dosing, i.e., when a subject permanently stops taking the study treatment before the last dose (the Week 51 dose). Reasons for mandatory study treatment discontinuation are listed in Section 10.1.1. The primary reason for study treatment discontinuation must be recorded in the subject's CRF.

Subjects who discontinue study treatment must return for an End of Treatment Visit as soon as possible, but within 4 weeks after discontinuation of treatment. All assessments planned for the Week 52 Visit except the HRCT scan will be performed. If the End of Treatment Visit occurs in the visit window for the next scheduled visit, then the scheduled visit may serve as the End of Treatment Visit, and all assessments for the End of Treatment Visit should occur at that time. Subjects will go on to complete all remaining visits as scheduled, including the Week 52 and Safety Follow-Up Visits (see Table 2 for a list of assessments to occur at the End of Treatment and Safety Follow-Up Visits).

Note: A subject who misses 1 or more doses of study treatment should restart study treatment, receive all remaining doses, and complete all remaining study visits.

See Section 10.2 for information related to the withdrawal of subjects from study.

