3 STUDY DESIGN

This is a Phase 2b randomized, double-blind, placebo-controlled study designed to evaluate the efficacy, safety, PK, and tolerability of BG00011 in subjects with IPF. Approximately 290 subjects who meet inclusion/exclusion criteria will be stratified by background therapy status (subjects receiving background therapy and subjects not receiving background therapy) and randomized in a 1:1 ratio of BG00011 to placebo (**Error! Reference source not found. of the protocol**).

Subjects will receive weekly injections of BG00011 or placebo for 52 consecutive weeks (a total of 52 doses). Study duration for an individual subject is approximately 65 weeks, including a Screening Visit up to 5 weeks prior to the first dose of study treatment, a Placebo-Controlled Treatment Period of 52 weeks, and a Safety Follow-Up Visit 8 weeks after the end of the Treatment Period.

A schematic of the study design is provided in Figure 1. Additional details on the study design and the schedule of study assessment is provided in the full protocol. Due to the early termination of the study, no interim analysis will be performed. This change supersedes the interim analysis planned in the schematic of the study design in the protocol.

Figure 1: Schematic for Study 203PF203

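### The exposure formula stops at the last dose date, so a subject who takes all 52 doses on schedule is credited with 51.14 weeks and misses the 52-week category

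*SAP*

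**What the plan says.** SAP 6.5 calculates duration of exposure in weeks as "date of the last dose – date of the first dose +1)/7". The result is summarised as a continuous variable and as "cumulative duration of exposure categories: at least 4, 8, 12, 16, 20, 26, 32, 38, 44, 52 weeks". The section gives no rounding rule and adds no dosing interval after the last injection.

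SAP section 3 describes weekly injections "for 52 consecutive weeks (a total of 52 doses". Protocol 7.1 fixes the start: "The first dose will be administered at the Baseline (Day 0) Visit". The schedule of events in protocol 5.2 has the remaining doses given "once weekly from Week 1 (second dose) through Week 51 (final dose". Protocol 10.1 agrees, defining discontinuation as when a subject "permanently stops taking the study treatment before the last dose (the Week 51 dose".

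SAP section 1 says the plan was developed from protocol version 1 and that version 2 was not implemented. The dose timing above stands in version 1. Version 1 section 11.2 does not allow the dosing schedule to be modified.

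**The concern.** The formula counts calendar days from first to last injection inclusive. That is a complete count for a drug taken daily. For a weekly drug it credits the last dose with one day rather than the seven-day interval it covers. The category labels, however, follow the planned regimen, in which 52 doses make 52 weeks. The formula and the labels are therefore one dosing interval out of step.

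At stake is how the exposure table reads. The study was stopped on a safety imbalance and SAP section 1 says the safety data will be analysed in full, so the table is the context in which those data are read. As written, its top row would leave out every subject who followed the regimen to the letter and admit only those whose last dose was late. In the same section, an on-schedule completer scores 52/52 = 100% compliance.

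**Working it through.** **Inputs**

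- First dose: Day 0 (protocol version 1, section 7.1).
- Interval: 7 days; planned doses: 52 (SAP section 3).
- Final dose: Week 51 (protocol version 1, sections 5.2 and 10.1).
- Duration: (last dose date − first dose date + 1)/7 (SAP 6.5).

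**Timing of the final dose.** Dose k falls 7(k − 1) days after the first. Dose 52 falls at 7 × 51 = 357 days, which is Week 51 and reproduces the schedule of events.

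**On-schedule completer.** (357 + 1)/7 = 358/7 = 51.14 weeks. This is below 52, and rounding to the nearest week would give 51.

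**When the formula reaches 52.** It needs (d + 1)/7 ≥ 52, so d ≥ 363 days. That is 363 − 357 = 6 or more days after the due date.

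**Lower cut-offs.** N on-schedule doses give (7(N − 1) + 1)/7 = N − 1 + 1/7 weeks.

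| Cut-off N (weeks) | Weeks credited for N doses, SAP formula | On-schedule doses needed to enter the row | Weeks credited for N doses, +7 |
|---|---|---|---|
| 4 | 3.14 | 5 | 4 |
| 8 | 7.14 | 9 | 8 |
| 26 | 25.14 | 27 | 26 |
| 44 | 43.14 | 45 | 44 |
| 52 | 51.14 | 53 | 52 |

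The other cut-offs behave in the same way. The top row would need a 53rd weekly dose, which the regimen does not contain.

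**Who changes category.** With +7, a subject enters row N when d ≥ 7N − 7; with +1, when d ≥ 7N − 1. Only subjects whose last dose falls between 7N − 7 and 7N − 2 days after the first are classified differently, a span of six days at each cut-off. For on-schedule dosing these are the subjects with exactly N doses.

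**Continuous summary.** The difference between the two formulas is (7 − 1)/7 = 6/7 week for each subject, before any cap.

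**The case against.** First-to-last-dose inclusive is an explicit, reproducible convention, and its +1 matches the study-day rule in SAP 6.1.1.3. The +7 form is a convention too. Protocol 4.4.3 reports a terminal half-life of about 174 hours at doses below 3.0 mg/kg, so neither formula measures how long drug is present. This stands: the formula could be kept if it were labelled as time to last dose and the cut-offs were chosen to fit. It does not rescue the present pairing, in which the label takes a 52-dose regimen as 52 weeks and the formula does not.

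The consequence is also limited. The study stopped early, and the documents do not say how many subjects took all 52 doses. Study completion is reported separately under disposition (SAP 6.2), and full dosing shows in the compliance summary. No statistical testing is done on safety data (SAP 8.1), and no efficacy model visible in the SAP uses this variable. All of this stands.

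A reader might infer that the 52-week category can never be reached. That is too strong. Protocol 10.1 tells subjects who miss doses to restart and take all remaining ones, and a final dose 6 or more days late would qualify. A reader of protocol version 2 might also point to its +2-day dosing window. That version was not implemented, and the window would give only (359 + 1)/7 = 51.43 weeks.

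**Conclusion.** The point holds as a minor but definite error in the descriptive exposure summary. A subject who takes all 52 doses on schedule is credited with 51.14 weeks and excluded from the 52-week row. A subject with exactly N on-schedule doses falls one category short at each lower cut-off N, and the continuous summary is 6/7 week lower per subject than the dosing periods covered. This rests on the version 1 dose schedule, on no rounding being applied, and on each weekly dose being taken to cover seven days.

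Two stronger readings are not supported:

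- **Every subject is under-counted in the categories.** Each subject's continuous value is lower, but only those whose last dose falls in the six-day span before a cut-off change row.
- **Adverse event rates are inflated.** SAP 8.2 lists a table of TEAE incidence rates but gives no person-time denominator and no link to section 6.5. What it defines are counts of subjects and proportions of the analysis population. It follows TEAEs to the last follow-up visit, so time on drug is not the obvious denominator. The offset would carry into those rates only if this duration were used, which the SAP does not state.

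**What to change.** In SAP 6.5, replace the formula with (date of last dose − date of first dose + 7)/7, capped at the date of death or last contact. N on-schedule doses then give N weeks, before any cap, and the existing category labels can stay.

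The minimum alternative is to keep the formula, state that exposure is counted to the date of the last dose, and redefine the cut-offs to match, for example by number of weekly doses received.

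The cost is a small text edit and a matching programming change, with no new assessments. The cap is a new rule, so it needs its own sentence and the two dates in the derivation. SAP 1.1 has the plan finalised before the Part I lock and any later change documented in a new version, so the edit should be made before that lock or recorded as a revision.

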6.6 Protocol Deviations

Protocol deviations identified during site monitoring will be captured in a Protocol Deviation Log and will be categorized as major or minor deviations based on protocol deviation

classification prior to the final database lock. The major protocol deviations will be summarized and listed. The minor protocol deviations will also be listed. All summaries for protocol deviations will be presented by background therapy status and treatment group.

6.7 Multiplicity Adjustment

No multiple comparison adjustments are planned and all inferential analyses performed will be interpreted nominally.

7 Efficacy Analysis

7.1 General considerations

All efficacy analyses will be performed on the MITT population, unless otherwise specified. For each endpoint, additional conditions may apply to the definition of the population for the analysis. Subjects will be analyzed in the groups to which they were randomized.

7.2 Analysis of Primary Endpoint

7.2.1 Primary Analysis

The estimand of the primary analysis is the mean difference of the change from baseline in FVC (expressed in mL, at each week 26 or week 38) between treatment and placebo group in the MITT population [[ICH E9 \(R1\) Addendum 2014, 2017](#)]. Data will be censored when subject experienced intercurrent event (i.e. death and/or lung transplantation and/or treatment discontinuation) and prematurely discontinued the study treatment. The estimate of this analysis reflects the treatment effect of BG00011 if the drug were taken as directed [de jure efficacy estimand].

Due to the study early termination, the estimand will assess the mean difference of the change from baseline in FVC (mL) at week 26 and 38 based on the data availability and visit times of interest. Both change from baseline in FVC (mL) at weeks 26 and 38 are the continuous secondary efficacy endpoints. If less than 20 subjects (i.e. <20 subjects) had non-missing measurements at either visit time of interest, the mean difference comparison will not be performed at that visit time due to the insufficient data.

A random coefficients linear regression model will be used as the primary analysis where the change from baseline in FVC (mL) is the outcome variable assuming linear decline in lung function over time. The model will include random coefficients for intercept and slope (time), and fixed-effect terms for treatment, randomization stratum (background therapy), age, and baseline FVC along with treatment-by-time interaction and background therapy status-by-time interaction. In this model, time is considered as a continuous variable.

An unstructured variance covariance structure will be used to model the within-patient measurements variability. If the unstructured covariance structure matrix results in a lack of convergence, first-order autoregressive, AR(1), covariance structure will be used. The Kenward-Roger approximation will be used to estimate the denominator degrees of freedom.

If a subject who experiences unscheduled visit(s) for acute exacerbation of IPF and has non-missing FVC measurement(s), those unscheduled FVC measurement(s) will be included in the primary analysis.

In the primary analysis, missing data are assumed to be missing at random (MAR) [[Rubin 1976](#)]. For subjects who experienced intercurrent event (i.e. death and/or lung transplantation and/or treatment discontinuation), subject's post intercurrent event data will be censored and then imputed based on individual's estimated rate of worsening of lung function prior to treatment discontinuation, similar to linear extrapolation because of the linear assumption of the statistical model.

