Background therapy for IPF with pirfenidone or nintedanib will be allowed during the study. The subject must be on a stable dose of either medication for at least 8 weeks prior to randomization. The subject is not to be on both medications simultaneously and should not initiate background therapy during the study. In cases where the Investigator feels that background therapy is clinically indicated, this therapy can be started, but the initiation of background therapy during the study will be considered a protocol deviation. While participating in the study, every effort should be made to maintain the subject on a stable dose of background therapy, and dosing should not exceed the labeled maximum dose. However, background therapy dosing may be adjusted or discontinued by the subject's pulmonary care physician. The subject may continue in the study if background therapy is discontinued. Subjects will maintain a diary to record background therapy dosing and any adjustments made in their therapy.

Assessment of pulmonary function by spirometry (FVC, FEV₁, and FEV₁/FVC) before and after bronchodilator use will be performed at Screening. During the Treatment Period, spirometry evaluation (without bronchodilator use) will be performed at the Baseline Visit and at all Treatment Period visits (excluding Day 5). Other PFTs include DL_{CO} (corrected for Hgb), to be

CONFIDENTIAL

The information contained herein may not be used, disclosed, or published without the written consent of Biogen MA Inc.

assessed at Screening, Baseline, and Weeks 4, 8, 16, 26, 38, and 52; and total lung capacity and residual volume, to be assessed by full-body plethysmography at Baseline, Week 26, and Week 52. All PFT results will be reviewed centrally.

An independent data safety monitoring board (DSMB) will review the unblinded safety and available PK data throughout the study (at least quarterly) to assess the overall safety profile (see Section 19.2.2 for additional information).

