16.2.2.2. Analysis of the Primary Endpoint

The population for the primary endpoint analysis will be subjects in the ITT population with a baseline and at least 1 postbaseline FVC measurement.

The primary efficacy outcome variable is the yearly rate of change in FVC (actual value, expressed in mL, over 52 weeks). The primary endpoint will be analyzed using a random coefficients linear regression model, with an absolute change in FVC as the outcome variable

CONFIDENTIAL

The information contained herein may not be used, disclosed, or published without the written consent of Biogen MA Inc.

assuming linear decline in lung function over time. The model includes random coefficients for intercept and slope (time), and fixed-effect terms for treatment, randomization stratum (background therapy), age, and baseline FVC. Interaction terms in the model will be the interaction between treatment and time, and the interaction between pirfenidone or nintedanib and time.

Every effort should be made to reduce the amount of missing data. In the analysis of the primary endpoint, missing data will be assumed to be missing at random. An unstructured variance-covariance structure will be used to model the within-patient measurements variability. If it fails to converge, an AR(1) structure will be used. The variance-covariance matrix, modeled to estimate the interindividual variability, is considered to have a variance components structure. Because the statistical model assumes a linear decline in lung function over time and, hence, implicitly imputes missing data based on individual's estimated rate of worsening of lung function prior to treatment discontinuation, similar to linear extrapolation. If a subject who was not on background therapy at randomization initiates treatment with background therapy during the study, the subject's data collected after the initiation of background therapy will be excluded from the primary analysis. However, a sensitivity analysis that includes the excluded data will be performed.

Support analyses for the primary endpoint includes:

1. Analysis using multiple imputation with pattern mixture models will be carried out. Details of sensitivity analysis and assumptions for different pattern will be described in the statistical analysis plan (SAP).

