16.9. Sample Size Considerations

The sample size calculation is based on the annual declining rate in FVC (mL/year). With 145 subjects randomized per arm, and assuming a 15% dropout rate over a 1-year treatment period, the study has approximately 80% power to show that the BG00011 treatment arms differentiate from the arm without BG00011 at a 2-sided 15% α level, given a treatment effect of 82.5 mL/year with a common standard deviation of 280 mL. The calculation is based on the assumption that the FVC decline rate in subjects receiving placebo and no background therapy is 220 mL/year, and in subjects receiving background but no BG00011 therapy it is assumed to be 110 mL/year. A 60% reduction in the FVC decline rate in the subjects receiving placebo would be a treatment effect of 132 mL/year. A 30% reduction in the FVC decline rate in subjects receiving background therapy would be a treatment effect of 33 mL/year. With the assumption that 50% of each type of subject are randomized in the study, the combined treatment effect is approximately 82.5 mL/year. The 15% dropout rate for this study was estimated based on prior experience for the placebo arms in the Phase 3 studies for nintedanib and pirfenidone [King 2014; Richeldi 2014].

CONFIDENTIAL

The information contained herein may not be used, disclosed, or published without the written consent of
Biogen MA Inc.

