7.3.3 Analysis of Time-to-Event Endpoints

The time-to-event endpoints will be analyzed using survival analyses methods. The Kaplan-Meier curve and number of subjects at risk at each visit will be presented. The proportion of subjects who progressed in each treatment group will be summarized.

Time to event will be analyzed by a cox proportional hazards model with terms for treatment (BG00011 vs. placebo) and randomization stratification factor. A stratified log-rank test will be used to compare the 2 treatment groups using randomization stratus as the stratification factor. The progression will be summarized descriptively for each stratum.

Censoring rules will be applied for all time-to-event endpoints, unless otherwise specified. Subjects who do not experience an event by early termination, will be censored at the date of last assessment during the treatment period. The start date for calculation of day to censor or event will be the date of first dose. If a subject who was not on background therapy at randomization initiate treatment with background therapy during the study, the study will be censored at the time of new background therapy initiation. If a subject who was on background therapy at randomization stop background therapy during the study, the study will be censored at the time of the background therapy stopped.

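### SAP 7.2.1 drops, without a reason, the protocol's exclusion of FVC measured after a subject randomized off background therapy starts pirfenidone or nintedanib

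*SAP*

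**What the plan says.** **Protocol.** Section 16.2.2.2 covers a subject who was off background therapy at randomization and later starts it: "the subject's data collected after the initiation of background therapy will be excluded from the primary analysis". The next sentence adds the counterpart: "However, a sensitivity analysis that includes the excluded data will be performed". The wording is the same in version 1, on which the SAP is built, and in version 2, which was not implemented. Version 1 Section 7.1 discourages such starts, but says that where the investigator finds background therapy clinically indicated, "this therapy can be started, but the initiation of background therapy during the study will be considered a protocol deviation". Version 1 Section 10.1.1 does not list a start among the reasons for mandatory discontinuation of study treatment.

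**SAP, FVC.** Section 7.2.1 sets the censoring rule: "Data will be censored when subject experienced intercurrent event (i.e. death and/or lung transplantation and/or treatment discontinuation) and prematurely discontinued the study treatment". It describes the target this way: "The estimate of this analysis reflects the treatment effect of BG00011 if the drug were taken as directed [de jure efficacy estimand". The last paragraph of 7.2.1 repeats the same three events, and the complementary analysis in 7.2.3 uses the same list. The MMRM in 7.2.2 has no rule for started background therapy. Section 7.3.1.1 applies all three analyses to percent predicted FVC.

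**SAP, time to event.** Section 7.3.3 does address the event: "If a subject who was not on background therapy at randomization initiate treatment with background therapy during the study", follow-up is censored at that date. It also censors when a subject stops background therapy.

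**Precedence.** SAP Section 1 states that the SAP supersedes the protocol's statistical considerations.

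**The concern.** The sponsor's own rule for a foreseeable event has disappeared from the primary endpoint but survives for time to progression, one component of which is a fall in percent predicted FVC. Because the SAP takes precedence, a programmer following it would keep FVC values recorded under a newly added antifibrotic.

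The model would not correct for this. Its background term is the randomization stratum, and the status-by-time interaction is not defined as time-varying, so a starter appears to be modelled as off background throughout.

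Two things are at stake. First, the estimate no longer matches the protocol's primary analysis, and the 'as directed' label does not say that added antifibrotic therapy is included. Second, the sensitivity analysis that would have shown the influence of these data is gone. The primary and complementary analyses differ only over death, transplantation and treatment discontinuation, so comparing them says nothing about started background therapy.

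**Working it through.** **Reproducing the plan's power** (Protocol 16.9, SAP 4)

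- Evaluable per arm: 145 × 0.85 = 123.25.
- Standard error: 280 × √(2/123.25) = 35.7 mL/year.
- Power at two-sided 15% for 82.5 mL/year: Φ(82.5/35.7 − 1.44) = 0.809. The stated figure of about 80% is reproduced.
- Stratum mix: 0.5 × 132 + 0.5 × 33 = 82.5 mL/year, as stated.

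**Planning slopes.** The documents assume 220 mL/year for placebo off background, and "in subjects receiving background but no BG00011 therapy it is assumed to be 110 mL/year". Subtracting the assumed effects of 132 and 33 mL/year gives the BG00011 slopes.

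| | Off background | On background | Change on starting |
|---|---|---|---|
| Placebo | 220 | 110 | 110 mL/year |
| BG00011 | 220 − 132 = 88 | 110 − 33 = 77 | 11 mL/year |

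**Decline masked in one subject by Week 38, start at Week 13 (assumed)**

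- Placebo: 110 × 25/52 = 52.9 mL.
- BG00011: 11 × 25/52 = 5.3 mL.

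**Planned differences at Week 38**

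- Overall: 82.5 × 38/52 = 60.3 mL.
- Off-background stratum: 132 × 38/52 = 96.5 mL.

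**Effect on the group difference.** The documents give no start rates. Assume 10 to 30 percentage points more starters on placebo in the off-background stratum, all at Week 13, and count the excess only.

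- In the stratum: 0.10 × 52.9 = 5.3 mL to 0.30 × 52.9 = 15.9 mL.
- Overall at a 50:50 mix: 2.6 to 7.9 mL, which is 4% to 13% of 60.3 mL.

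The same excess on BG00011 would move the overall difference by only 0.5 × 0.10 × 5.3 = 0.3 mL to 0.5 × 0.30 × 5.3 = 0.8 mL.

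**Other assumed patterns** (full planned size over 52 weeks, simple averaging of slopes)

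| Starters, placebo / BG00011 | Start | Combined effect (mL/year) | Power |
|---|---|---|---|
| None | – | 82.5 | 0.809 |
| 5% / 5% | mid-year | 81.3 | 0.799 |
| 10% / 10% | mid-year | 80.0 | 0.789 |
| 20% / 10% | mid-year | 77.3 | 0.766 |
| 30% / 10% | 3 months | 70.5 | 0.705 |

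Example, 10% in both arms: placebo 220 − 0.10 × 0.5 × 110 = 214.5; BG00011 88 − 0.10 × 0.5 × 11 = 87.45; combined 0.5 × 127.05 + 0.5 × 33 = 80.0. These powers describe the planned 145 per arm, not the terminated study.

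**The case against.** The strongest reply has four parts.

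1. **The label refers to BG00011.** Censoring at study-drug discontinuation while keeping data after a change in concomitant therapy is a permissible mixed strategy, and the SAP says openly that it replaces the protocol's statistics. This stands in part: the SAP could adopt that strategy. But it does not state it, gives no reason, and takes the opposite course in 7.3.3.

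2. **The effect may be small.** The 3 to 8 mL at Week 38 annualizes to 2.6 × 52/38 = 3.6 to 7.9 × 52/38 = 10.8 mL/year, or 0.1 to 0.3 of the planned standard error of 35.7 mL/year. With 5% to 10% starting at mid-year in both arms the loss is 1 to 3 mL/year. SAP 6.7 makes all inference nominal. This stands, and it limits the importance of the point.

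3. **Starts are partly visible.** Concomitant medication is summarized by treatment group (SAP 6.4). Deviations are listed, and major ones summarized, by background status and treatment group (SAP 6.6). Frequency may be recoverable, but the influence on FVC is not.

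4. **Version 1 does not expressly say that a starter stays on assigned treatment.** That sentence is in version 2. Version 1 Section 7.1 only allows continuation in the study when background therapy is discontinued, and version 1 Section 11.5.1.1 repeats the prohibition without the exception in 7.1. Continued dosing is therefore implied by the discontinuation list, not stated. This is enough to show that a start does not by itself trigger the SAP's censoring.

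**Conclusion.** The point holds as an unexplained departure from the protocol. SAP 7.2 omits both the exclusion and its paired sensitivity analysis, nothing else in the readable FVC analyses removes the post-start data, and the same SAP keeps the rule for time-to-event endpoints. It should be settled before the Part I lock, but it is not shown to change the conclusion.

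The size rests on the planning slopes, the 50:50 mix, a uniform Week 13 start and an assumed excess of placebo starters. On those assumptions the overall Week 38 difference falls by about 3 to 8 mL of 60 mL.

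A reader might go further in four ways that the documents do not support:

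- **That subjects cross over.** They add background therapy; they do not change arm.
- **That therapy was started because the subject was declining.** The stated condition is clinical indication. Decline as the trigger is plausible but inferred.
- **That harm from BG00011 would be masked by a similar amount.** On planning rates a BG00011 starter masks about 5 mL, and the documents give no slopes under harm. The study was stopped on a safety imbalance, so masking of harm cannot be ruled out, but it cannot be sized.
- **That 53 mL against 60 mL means the effect is nearly cancelled.** The first figure is for one subject and the second is a group mean difference.

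**What to change.** - In SAP 7.2.1, including its last paragraph on post-event data, add initiation of pirfenidone or nintedanib by a subject not on background therapy at randomization as an event after which FVC is excluded from the primary analysis, as in Protocol 16.2.2.2.
- State the same rule for the MMRM in 7.2.2 and for percent predicted FVC in 7.3.1.1. Section 7.3.1.1 also uses the 7.2.2 model for DLco and TLC, so say whether the rule carries over to them.
- Restore the protocol's sensitivity analysis as the primary model with only the post-initiation FVC added back. Keep it separate from 7.2.3: that analysis also adds post-discontinuation data, so it would differ from the primary in two respects and could not isolate this one.
- State how stopping of background therapy is handled for FVC, consistently with 7.3.3.
- Report the number and timing of starts by arm.
- If the omission was deliberate, say so, give the reason and reword the 'as directed' label.

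The cost is a few sentences, one data flag and one further model run. Section 7.3.3 already needs the start dates, and SAP 1.1 allows documented revisions. The downside is slightly fewer FVC values in the primary analysis, with correspondingly more reliance on its missing-at-random and linear-decline assumptions for starters.
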